#### **9.10.10. Study Drug Dispensation and Collection**

Study drug will be dispensed to the patient and collected from the patient as indicated in [Table 3](#). The patient will be dispensed 1 or more treatment kits at Day 1, Week 4, Week 24, and every 24 weeks thereafter for the duration of the study. Dispensed treatment kits from each visit should be returned to the site for collection at the subsequent visit.

#### **9.10.11. Telephone Contact**

Patients will be contacted by telephone as indicated in [Table 3](#). Patients will be asked about their body weight and other signs of fluid retention, as well as AEs and any changes to concomitant medications. If fluid retention is suspected, the patient must be brought into the clinic and evaluated by the investigator as soon as possible, as detailed in [Section 9.1.1](#).

#### **9.10.12. Adverse Event Collection**

Patients will be observed for general appearance, presence of illness or injury, or signs indicative of a concurrent illness as indicated in [Table 3](#). Patients must be instructed to volunteer any information regarding AEs on or after the first dose of study drug or query the patients with an open question regarding any AEs they may be experiencing (*e.g.*, “How have you been feeling

since your last visit?"). Any findings are to be documented. Patients must be asked if they have been hospitalized, had any accidents, used any new medications, or changed concomitant medication regimens (including prescription drugs, over-the-counter medications, vitamins, herbal products, and minerals). Responses must be documented in the source documents.

#### **9.10.13. Clinical Chemistry**

Samples will be collected for clinical chemistry analyses as indicated in [Table 3](#). Clinical chemistries will be analyzed locally and should include those routinely monitored per patient's standard of care.

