### **5.2.3. Transaminase and Gamma-Glutamyl Transpeptidase Elevations**

In clinical studies of bardoxolone methyl, almost all patients had increases of transaminase enzymes above baseline upon initiation of treatment, which followed a consistent pattern. These increases were not associated with elevations in bilirubin or other signs of liver toxicity. In a large Phase 3 study that enrolled 2185 patients with type 2 diabetes and stage 4 CKD (BEACON), fewer hepatobiliary SAEs were observed in the bardoxolone methyl arm than in the placebo arm. The elevations begin immediately after initiation of treatment or an increase in dose; they peak approximately two to four weeks later. In most patients, transaminase elevations were mild, but approximately 4% to 11% of patients experienced an elevation greater than 3X the upper limit of normal (ULN). The elevations resolved to levels less than the ULN in most all patients with elevations, within two weeks after peak values while patients continued taking study drug. Patients who experienced elevations to greater than 3X the ULN sometimes required additional time to resolve. While some patients have had elevations to above 3X the ULN, persistent elevations to above 3X the ULN have not been observed, and the elevations did not recur once resolved, unless caused by other factors.

Bardoxolone methyl regulates gamma-glutamyl transpeptidase (GGT), a known Nrf2 target gene. In clinical studies, low level GGT elevations during treatment were common, mild, and typically lasted longer than alanine aminotransferase (ALT)/aspartate aminotransferase (AST) elevations. Bilirubin levels in patients experiencing transaminase or GGT elevations due to treatment with bardoxolone methyl either remained at baseline levels or decreased. The ALT, AST, and GGT elevations were generally self-limiting in patients who continued treatment with study drug.

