### **8.3. Patient Discontinuation and Termination**

Patients have the right to discontinue study drug or withdraw from the study at any time for any reason, without prejudice to their medical care. Furthermore, the investigator may discontinue a patient from study drug. Consultation with the medical monitor should occur prior to study drug discontinuation or withdrawing a patient from the study. The reason for a patient's discontinuation from study drug or study termination will be recorded in the electronic case report form (eCRF).

Discontinuation refers to a patient's stopping administration of study drug and all study assessments and visits. Reasons for study drug discontinuation may include the following:

- Occurrence of an AE or change in medical status that will lead the investigator to be concerned about the patient's welfare;
- Administrative reasons (*e.g.*, inability to continue);
- Sponsor termination of the study;
- Voluntary withdrawal;
- Females who become pregnant during the study;
- Premature termination or suspension of an investigational site;
- Loss to follow-up;
- Death;
- Withdrawal of consent.

Patients must discontinue study drug if any of the following occur.

- ALT or AST > 8X ULN;
- ALT or AST > 5X ULN for more than 2 weeks;
- ALT or AST > 3X ULN and (total bilirubin > 2X ULN or International Normalized Ratio [INR] > 1.5);
- ALT or AST > 3X ULN with the appearance of fatigue, nausea, vomiting, right upper quadrant pain or tenderness, fever, rash, and/or eosinophilia (> 5%).

Patients who discontinue from the study will be asked to complete the End-of-Study procedures noted in [Table 3](#).

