#### **9.1.2. Management of Elevated Transaminase Levels (ALT and/or AST)**

Transaminases should be monitored following patient's standard of care. Nearly all instances of elevated transaminases are expected to be asymptomatic. Transaminase levels (as well as total bilirubin [TBL], GGT, alkaline phosphatase, and INR) will be checked within 48 to 72 hours during an unscheduled visit if the following occurs:

- ALT or AST levels > 3X ULN.

Testing will be repeated every 72 to 96 hours until transaminase levels are below 3X the ULN for at least one week or until the patient withdraws consent.

Study drug administration will be permanently discontinued if any of the following occurs:

- ALT or AST > 8X ULN;
- ALT or AST > 5X ULN for more than 2 weeks;
- ALT or AST > 3X ULN and (TBL > 2X ULN **or** INR > 1.5);

- ALT or AST > 3X ULN with the appearance of fatigue, nausea, vomiting, right upper quadrant pain or tenderness, fever, rash, and/or eosinophilia (> 5%).

The hepatobiliary tree must be visualized (*e.g.*, ultrasound, magnetic resonance imaging) and assessed if a patient discontinues taking study drug secondary to elevated transaminase levels. Additional tests/studies may be warranted depending on the clinical presentation.

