9.4. Summaries of Laboratory Results

Laboratory data are summarized at baseline and at each time point by treatment analysis group (Section 4.5). Only values obtained within analysis study windows (Section 6.5.5) are included in by-visit summary statistics

Patients falling into the following four clinical meaningful categories are listed.

In addition, the number and percentage of patients in the following four clinical meaningful categories is summarized at each analysis visit by treatment analysis group (Section 4.5).

- BNP > 200 pg/mL
- BNP increase from baseline > 100%
- NT-proBNP > 1000 pg/mL
- NT-proBNP increase from baseline > 100%

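### Mandatory hepatic stopping limits rest on ALT/AST results whose measurement is left to local standard of care, and the SAP counts no patient against those limits

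*Protocol*

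**What the plan says.** **The rule.** Protocol 8.3 introduces four hepatic criteria with "Patients must discontinue study drug if any of the following occur". Each starts from ALT or AST: above 8X ULN; "ALT or AST > 5X ULN for more than 2 weeks"; above 3X ULN with total bilirubin above 2X ULN or INR above 1.5; and above 3X ULN with listed symptoms or eosinophilia. Protocol 9.1.2 repeats the list under "Study drug administration will be permanently discontinued if any of the following occurs".

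**The measurement.** Protocol 9.1.2 opens with "Transaminases should be monitored following" the patient's standard of care. Protocol 9.10.13 defines the chemistry panel in the same way: "Clinical chemistries will be analyzed locally and should include those routinely monitored per" that standard. Table 3 schedules clinical chemistries at Day 1, Weeks 1, 2, 4, 6, 8 and 24, every 24 weeks and End of Study. Its footnote adds only that analysis is local.

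**The conditional work-up.** Once ALT or AST above 3X ULN is found, 9.1.2 requires transaminases, bilirubin, GGT, alkaline phosphatase and INR within 48 to 72 hours, then repeats every 72 to 96 hours until levels have stayed below 3X ULN for a week.

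**The analysis.** SAP 9.4 summarises laboratory data by visit without naming analytes. It then says "Patients falling into the following four clinical meaningful categories are listed", and also counts those categories by visit. They are BNP above 200 pg/mL, NT-proBNP above 1000 pg/mL, and a rise of more than 100% in either.

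**The concern.** A compulsory stopping rule works only if its input is measured. Here the obligation to stop is fixed by the protocol, while the obligation to measure is handed to local practice. Protocol 9.1.2 expects nearly all transaminase rises to be without symptoms, so asking patients how they feel will not replace the blood test.

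Reporting is the second issue. The study exists to collect long-term safety data on a drug with a described transaminase effect (Protocol 5.2.3). As planned, the report could not say how many patients reached the protocol's own limits, or out of how many tested. A reader could not tell an absence of elevations from an absence of tests.

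**Working it through.** The plan gives no figure to reproduce on this point. The check compares the passages and then follows a result through the SAP's rules.

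1. **Is ALT or AST required at any scheduled visit?**
   - Protocol 8.3 and 9.1.2: stopping is obligatory.
   - Protocol Table 3: visits are fixed, analytes are not named.
   - Protocol 9.10.13: the panel is whatever standard of care includes.
   - Protocol 9.1.2: transaminase monitoring follows standard of care.
   - Protocol 11.3 also describes laboratory values as monitored under standard of care.

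   No section names ALT or AST as required at a scheduled visit. The first required ALT/AST test is the 48 to 72 hour recheck, which needs an earlier ALT or AST above 3X ULN to start it.

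2. **Are bilirubin and INR in the same position?** No. They enter one rule, and only jointly with ALT or AST above 3X ULN. At that point 9.1.2 requires both. Their availability depends on the trigger being seen, so the gap is in detecting ALT/AST.

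3. **Does any SAP output compare results with the limits?** The four categories in SAP 9.4 are two for BNP and two for NT-proBNP, so none of the four is hepatic. Total bilirubin appears in the SAP only as an abbreviation, and no scaling to ULN is described. Laboratories are local, so a mean of raw values mixes different reference ranges.

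4. **Would a peak survive the visit windows (SAP 6.5.5)?** Only the value nearest the target day is kept in each window, and SAP 9.4 uses only in-window values.
   - The Week 4 window is Days 22 to 35, which is 35 − 22 + 1 = 14 days. Repeats every 4 days give 3 or 4 results in it; every 3 days, 4 or 5. One of these 3 to 5 results is summarised, chosen by date and not by height.
   - Between Week 8 (ends Day 70) and Week 24 (starts Day 140), Days 71 to 139 fall in no on-treatment window: 139 − 71 + 1 = 69 days.
   - Between Week 24 (ends Day 196) and Week 48 (starts Day 308), the gap is Days 197 to 307: 307 − 197 + 1 = 111 days. The same gap recurs in each later 168-day cycle.

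   Scheduled visits held near their target days fall inside the windows. Unscheduled repeats are the results most often lost, and they are where a hepatic episode is documented. They go to listings only.

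5. **Can the duration rule be read from the by-visit tables?** The rule of more than 5X ULN for more than 2 weeks needs successive values in the same patient. A mean, median or range by visit cannot show it.

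6. **Could the table be produced?** Protocol 14.4 already has sites supply laboratory normal ranges. SAP version 2.0 (05-Jun-2020) describes itself as finalised before the initial database lock.

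**The case against.** **Loose wording, not conflict.** The sentence on transaminases can be read as saying that they are monitored, with standard of care settling only the manner. Chemistry draws are frequent early on, and many local panels may include ALT and AST. This is fair. The documents do not show that any site omitted these tests, and a reader should not infer that one did. What stands is that the text does not require them.

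**Bilirubin and INR.** A reader might infer that all four inputs are equally unassured. The conditional work-up in 9.1.2 rules that out.

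**Adverse event tables.** Protocol 11.6 makes a laboratory change an adverse event if action is needed, and stopping drug is an action. Such stops should therefore appear in the SAP 9.1.2 table of events leading to permanent discontinuation. This stands in part. The event may be coded under a diagnosis, entry depends on the investigator's judgement, and there is no denominator of patients tested. A patient who met a limit but continued need not appear there.

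**Outside the endpoint.** ALT and AST are not in the primary safety endpoint, and Protocol 12.2.1 lists only BNP and NT-proBNP as laboratory variables. That is correct, although the synopsis lists laboratory results among the safety criteria. Limits that oblige a patient to stop treatment merit a count in a safety report.

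**Size.** It is tempting to apply the 4% to 11% rate of elevations above 3X ULN in Protocol 5.2.3 to the maximum of 366 patients (366 × 0.04 = 14.6; 366 × 0.11 = 40.3) and then assume some share untested. The documents do not support this as a count of missed stops. Exceeding 3X ULN alone leads to retesting, not stopping. Protocol 5.2.3 ties the rises to starting treatment or raising the dose, while all LARIAT patients (up to 166 of the 366) had already received the drug (SAP 4.5). The total of 366 is a ceiling, and no source gives the untested share.

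**Conclusion.** The point holds in two parts. First, the protocol makes stopping mandatory on ALT/AST limits without requiring that ALT or AST be measured at scheduled visits, so a site can comply and not observe the trigger. Second, the SAP has no output that sets hepatic results against those limits. Its by-visit rule keeps one unscaled local value per window and leaves gaps of 69 and then 111 days in which unscheduled results enter no by-visit summary.

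No number of affected patients can be given. It would need the share of patients without ALT/AST testing and the rate of meeting the actual stopping limits in this population, and the documents state neither. The conclusion rests on the wording alone, with one assumption: that standard of care may differ between sites in whether it includes ALT and AST.

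Termination on March 30, 2020 (SAP 6.6.4) limits what can be gained. Reconciling the protocol cannot supply tests that were not done. Reporting how many patients were tested, and how many met each limit, remained open when the SAP was finalised.

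**What to change.** **Protocol.** The sponsor must reconcile the discontinuation rules in 8.3 and 9.1.2 with the monitoring text in 9.1.2, 9.10.13 and Table 3. How to do so, and the clinical limits themselves, are for the sponsor. For this terminated study, it serves mainly to make the record consistent.

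**SAP 9.4.** Add one table, by treatment analysis group and overall:
- Express ALT, AST and total bilirubin as multiples of the ULN of the laboratory that ran the sample. INR, where measured, is compared with its limit directly.
- Give the number and percentage of patients ever meeting each limit already in Protocol 8.3.
- Use all on-treatment values, including unscheduled ones and those outside the visit windows. State how the more-than-2-weeks criterion is derived from successive values, and how symptoms are linked to the elevation for the fourth rule.
- Use the number of patients tested as the denominator and show it beside the number treated. This agrees with the reduced denominators in SAP 6.2.

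**Cost.** Local ULNs must be captured in the analysis data, drawing on the normal ranges sites already supply, and one table must be programmed. If ULNs are missing for some laboratories, those patients drop out of the denominator and their number should be stated.

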#### **9.10.14. N-Terminal Pro-Brain Natriuretic Peptide and Brain Natriuretic Peptide**

Samples will be collected for NT-Pro BNP and/or BNP as indicated in [Table 3](#). As recent exercise may affect BNP and NT-Pro BNP levels, patients must be allowed to rest for a minimum period of 1 hour following arrival at the clinic and prior to obtaining this blood sample. Similarly, this sample must be taken prior to the 6MWT or at least one hour after 6MWT. This sample must be taken with the patient in the same position at all appropriate visits, *e.g.*, sitting or semi-recumbent.

#### **9.10.15. 6-Minute Walk Test**

A 6-minute walk test (6MWT) will be performed by the patients as indicated in [Table 3](#). Unless otherwise indicated as described below, each test must be performed in strict accordance with the American Thoracic Society (ATS) guidelines ([ATS Statement 2002](#)) provided in [Section 19](#), Appendix 1. The appropriate language version will be applied for patients with a non-English informed consent. The walking course must be 30 m in length, except at sites granted prior Sponsor agreement.

Patients will rate their dyspnea and overall fatigue using the Borg scale (2004 version, provided in [Section 21](#), Appendix 3) prior to beginning and immediately following completion of each 6MWT as indicated in [Table 3](#).

The assessor of the 6MWT must not provide the patient with the results of the assessment once complete. A patient should wear the same or similar shoes for all 6MWTs. Additionally, if a patient uses a walking aid for the first test, this same aide should be used during all subsequent tests. The shoes worn and walking aid used for each 6MWT should be noted in source documents.

Patients who require supplemental oxygen with exercise may use their prescribed oxygen level during 6MWTs. If a patient's health status deteriorates during study participation and it is determined by a physician that the patient requires additional supplemental oxygen, the patient may continue study participation.

#### **9.10.16. WHO/NYHA Functional Class Assessment**

WHO/NYHA functional class will be assessed ([Section 20](#), Appendix 2) as indicated in [Table 3](#). To the extent feasible, the same evaluator should assess WHO/NYHA FC for a particular patient over the entire course of the study.

## 10. STUDY DRUG MATERIALS AND MANAGEMENT

### 10.1. Study Drug

Bardoxolone methyl capsules, 5 mg and 10 mg, will be used in this study.

### 10.2. Study Drug Packaging and Labeling

The study drug will be supplied in tamper-evident kits containing one 30-cc (5-mg capsules, 30 count), one 60-cc (5-mg capsules, 90 count), or one 100-cc (10-mg capsules, 90 count) high-density polyethylene bottle. Each bottle will utilize foil induction-seal liners and a child-resistant closure. Each bottle of study drug will contain 30 or 90 capsules of 5 mg or 10 mg strength bardoxolone methyl. Each bottle will also contain a desiccant insert that must not be ingested. Labeling on each kit bottle will contain at minimum the following information:

- Medication identification number;
- Protocol 402-C-1602;
- Caution Statement: New Drug – Limited by Federal Law to Investigational Use. Keep out of sight and reach of children;
- Control or lot number
- Store at 20° - 25°C (68° - 77°F), short term excursions allowed to 15° - 30°C (59° - 86°F);
- Reata Pharmaceuticals, Inc., Irving, TX.

A double panel label will be presented on the treatment bottle containing this and other information as well. Additionally, labeling in the relevant local languages for investigational medicinal product for use and distribution in the EU shall adhere to current Eudralex, Volume 4 Annex 13 guidance and requirements.

### 10.3. Study Drug Storage

The stability of the drug product has been and is currently being evaluated in ongoing studies.

Investigative sites must store the investigational product in a secure location with room temperature conditions of 20°C to 25°C (68°F to 77°F), with brief excursions allowed to 15°C to 30°C (59°F to 86°F).

### 10.4. Study Drug Administration

Please refer to [Section 9.10.9](#) for details on study drug administration. Clear instructions will be provided to the patient regarding the number and type of capsules to be ingested at each study drug administration time point listed in [Table 3](#). Patients must be instructed to continue taking study drug unless: (1) patient has been otherwise instructed by the investigator or (2) the patient has been formally discontinued from the study.

**10.5. Study Drug Accountability**

The investigator, or designee, will maintain a record of all study drug received, dispensed, and returned to the Sponsors' designee. No study drug shall be destroyed by the clinical site unless directed in writing to do so by the Sponsor's quality assurance department. Study drug bottles and any unused capsules should be returned to the study staff for eventual disposition by the Sponsor. The number of capsules returned at each visit will be recorded for each bottle in the kit.

**10.6. Study Drug Handling and Disposal**

At the conclusion of the study or in an instance of planned study drug replacement, the Sponsor or its designee will direct the site regarding the final disposition of study drug.

## **11. SAFETY ASSESSMENTS**

### **11.1. Safety Parameters**

To avoid inter-observer variability, every effort should be made to ensure that the same individual who made the initial baseline determinations will complete all safety assessments. Safety parameters will include vital sign measurements, physical examination results, AEs, SAEs, weight, and assessment of BNP and/or NT-Pro BNP.

### **11.2. Adverse and Serious Adverse Events**

#### **11.2.1. Definition of Adverse Events**

##### **11.2.1.1. Adverse Event**

An AE is defined as any untoward medical occurrence in a patient regardless of its causal relationship to study drug. An AE can be any unfavorable and unintended sign (including any clinically significant abnormal laboratory test result), symptom, or disease temporally associated with the use of the study drug, whether or not it is considered to be study-drug related. Included in this definition are any newly-occurring events or previous condition that has increased in severity or frequency since the administration of study drug.

All AEs that are observed or reported by the patient during the study (from time of administration of the first dose at the Day 1 visit until the final visit indicated in [Table 3](#)) must be reported, regardless of their relationship to study drug or their clinical significance.

##### **11.2.1.2. Serious Adverse Event**

An SAE is any AE occurring at any dose and regardless of causality that:

- Results in death;
- Is life-threatening;
- Requires inpatient hospitalization or prolongation of existing hospitalization;
- Results in persistent or significant incapacity or substantial disruption of the ability to conduct normal life functions;
- Is a congenital anomaly or birth defect in an offspring of a patient taking study drug;
- Is an important medical event.

The term "life-threatening" refers to an event in which the patient was at immediate risk of death at the time of the event. It does not refer to an event that hypothetically might have caused death if it were more severe.

Important medical events are those that may not meet any of the criteria defined above; however, they may be considered serious when, based upon appropriate medical judgment, they may jeopardize the patient and may require medical or surgical intervention to prevent one of the other outcomes listed in the SAE definition.

Pregnancy is not considered an AE; however, information will be collected for any pregnancies that occur during the study (from the time of the first dose of study drug until the final visit indicated in [Table 3](#), as appropriate). Certain pregnancy outcomes will require submission as an SAE (See [Section 9.8](#)).

The investigator is responsible for reporting to Reata or designee all AEs and SAEs that are observed or reported by the patient during the study (from the time of administration of the first dose of study drug until the final visit indicated in [Table 3](#), as appropriate), regardless of their relationship to study drug or their clinical significance.

The Sponsor, or the Contract Research Organization (CRO) on the behalf of the Sponsor, must be notified immediately regarding the occurrence of any SAE that occurs after the patient receives the first dose of study drug and throughout the study, regardless of study drug administration, including SAEs resulting from protocol-associated procedures, as defined in relevant legislation. The procedures for reporting all SAEs, regardless of causal relationship, are as follows:

- Record the SAE on the AE eCRF and complete the “Serious Adverse Event Report” form within the electronic database;
- In the event the electronic database is not functional, a paper SAE form will be available for the reporting of SAEs.

The Sponsor may request additional information from the investigator to ensure the timely completion of accurate safety reports.

All SAEs reported or observed during the study must be followed to resolution or until the investigator deems the event to be chronic or the patient to be stable. Reata or designee may contact the investigator to obtain additional information on any SAE which has not resolved at the time the patient completes the study.

